In an Egyptian study conducted by Radi et al. in 2021 on 60 primary molars, the mean survival rate of SMART restorations was 11.2 months higher than that restored with ART restorations, within a follow-up period of 12 months. Although there was a statistically significant decrease in all the tested clinical criteria success rate (spontaneous pain,

mobility, sensitivity to percussion and sinus or swelling) within both groups, with ( $P$ -value <0.001, effect size = 0.367) for the group treated with ART and ( $P$ -value <0.001, effect size = 0.187) for the group treated with SMART (Radi et al., 2021).

In China, a study was conducted by Jiang et al. in 2019 on 194 children, in which 101 children received SMART and 93 received ART. At 24-month follow-up, there was no significant difference between the ART restoration success rates of the two study groups ( $p > 0.05$ ). The success rate of these restorations was affected by the class of these restorations: Class I restorations had the highest success rate (~50 %), followed by Class V (~35 %), Class II (~15 %), and Class III (<10 %). Besides, the meantime used to place SMART restorations was shorter than that in ART restorations with 4.8 and 5.1 mins respectively ( $p = 0.006$ ).

In the same study, parents were asked to rate their satisfaction with their child's teeth using a 5-point scale (5=very satisfied, 1=very dissatisfied), and the Chinese version of the Early Childhood Oral Health Impact Scale (C-ECOHIS) was used to assess the children's OHRQoL before and 6 months after the restorative treatment. At the 6-month follow-up, the mean parental satisfaction score regarding their child's dental health status increased significantly ( $p<0.001$ ) from  $2.2 \pm 0.7$  to  $2.8 \pm 1.0$  in the SMART group and from  $2.3 \pm 0.8$  to  $2.7 \pm 0.9$  in the ART group. However, no significant changes ( $p>0.05$ ) in C-ECOHIS scores were found in either of the two groups after ART restoration placement (Jiang M et al., 2019).

There is a lack of clinical trials comparing ART and SMART restorations. Thus, it is suggested to compare the clinical outcome of both techniques and their impact on oral health related quality of life in preschool children.

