### **Study Sampling:**

#### **• Size formula**

The sample size was specified by using the G power test, assuming a statistical level of significance of 5% and power 80% with normal distribution, and 0.367 effect size calculated from means and standard deviation of 2 groups obtained from a previous study (Jiang et al., 2021). The original sample size will be 64 molars, and will be increased up to 80 with a possible dropout.

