#### **• Grouping**

- **Group A** the teeth will be restored by ART using high viscosity glass ionomer cement (GC Fuji IX )
- **Group B** the teeth will be treated with silver diamine fluoride 38%, and then restored by high viscosity Glass Ionomer cement (Fuji IX), both according to manufacturer instructions.

- **Inclusion Criteria:**

- Generally healthy children of ages 3 to 6 years old, who have at least 2 bilateral decayed primary molars with occluso-proximal carious dentin lesions (scores 4 or 5) according to the International Caries Detection and Assessment System (ICDAS II)
- Children with negative (Rating 2) and positive (Rating 3) behavior, according to Frankel's behavior rating scale

- **Exclusion Criteria:**

- Children with systemic diseases/conditions
- Children with definitely positive and negative behavior
- Teeth with signs of pulpal pathology (abscess, fistula, mobility)
- Teeth with very deep cavities
- Teeth with signs of irreversible pulpitis

- **Ethical Approval:**

Written informed consent should be signed by patients' parents before participation in the study.

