## **Statistical Analysis:**

Data analysis was carried out by using the statistical software SPSS (version 28, IBM SPSS statistics, USA. Based on the results of the Shapiro-Wilk test, most of the data were determined to follow a normal distribution. The significance level was set at  $p \leq 0.05$ . The qualitative data were presented as frequencies and percentages, whereas the quantitative data were presented as median, range, mean, and standard deviation values. Paired Samples

t-Test was used to compare the means of two related groups, it was used to assess changes in ECOHIS scores at baseline and after intervention. Fishers exact test was used to compare the outcomes between ART and SMART at a single time point. Categorical data like the relation between the success rate of both treatments and the type of the cavity was analyzed by using the Chi-Square Test of Independence. The significance level was set at  $p \leq 0.05$ .

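### The chi-square test of success by cavity type uses an undefined factor: if it means lesion class, eligible teeth have only one level; if it varies, the test ignores pairing of molars within child

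*Combined protocol and SAP*

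**What the plan says.** The inclusion criteria under Grouping require that a child has "at least 2 bilateral decayed primary molars with occluso-proximal carious dentin lesions (scores 4 or 5" on ICDAS II). No other lesion type is listed as eligible.

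The Statistical Analysis section gives, as an example of its handling of categorical data, "the relation between the success rate of both treatments and the type of the cavity", and says that this "was analyzed by using the Chi-Square Test of Independence". It does not list the types. It also does not say whether the table pools the two treatments or is drawn up for each one.

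The only classification by class in the document is in the Introduction, which reports an earlier trial that treated several restoration classes and found: "The success rate of these restorations was affected by the class of these restorations".

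Study design specifies a split-mouth trial, and Randomization assigns teeth to technique. On numbers, Size formula says: "The original sample size will be 64 molars, and will be increased up to 80 with a possible dropout". Cavity type appears in no aim, hypothesis or outcome definition, and nothing says that it is recorded or stratified on.

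**The concern.** A test of association needs a factor with at least two levels. Eligibility names one kind of lesion, while the analysis compares kinds of cavity. Taken together, either a named analysis is empty or the treated teeth are not fully described by the eligibility text. A reader of the results could not tell which.

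The second difficulty does not depend on how cavity type is read. In a split-mouth trial each child supplies at least two related molars. A chi-square test of independence on teeth takes every molar as a separate unit, so its p-value does not have its nominal meaning when molars from the same child enter one table. What is at stake is the interpretability of a subsidiary analysis and a clear account of which lesions were treated.

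**Working it through.** The plan gives no sample size, power or expected split for this test, so there is no figure to reproduce. The check is of the structure of the table.

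**Inputs**
- Lesion type named by eligibility: occluso-proximal only (Grouping).
- Outcome: success or failure, so two rows.
- Molars: 64, or 80 with allowance for dropout (Size formula).
- Design: split-mouth (Study design).

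**Reading 1: cavity type means lesion class**
1. Degrees of freedom = (rows − 1)(columns − 1).
2. With one class, df = (2 − 1)(1 − 1) = 0. Run on one-column tables, the routine returns a statistic of 0, df of 0 and p = 1 by default. That is not a test result.
3. Adding an empty second column does not help. Its expected counts are row total × 0 / N = 0, so the statistic is undefined.
4. Neither result depends on N, so 64 and 80 molars give the same answer.
5. Crossing with treatment does not rescue it. With one class, a table of treatment by success within class is simply the overall ART versus SMART table, which the plan already assigns to Fisher's exact test.

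**Reading 2: cavity type varies among treated teeth**
1. Assume two molars per child. Then 64 molars come from 64 / 2 = 32 children and 80 molars from 80 / 2 = 40. The test counts 64 or 80 independent units.
2. Let p be the success probability, ρ the correlation of success between the two molars of a child, and m the number of molars at each of two levels. The test takes the variance of the difference in success proportions as 2p(1 − p)/m.
3. If both molars of each child share a level, the variance is 2p(1 − p)(1 + ρ)/m. For ρ > 0 the test understates it and p-values are too small.
4. If each child has one molar at each level, the variance is 2p(1 − p)(1 − ρ)/m. For ρ > 0 the test overstates it and p-values are too large.
5. The documents give neither ρ nor the mix of the two patterns, so neither the size nor the direction of the error can be stated.

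**Sparseness of a replacement factor**
1. Treatment (2) × factor level (2) × success (2) makes 8 cells: on average 64 / 8 = 8 molars per cell, or 80 / 8 = 10.
2. If about a tenth of molars were at the rarer level (an assumed split), that level would hold about 6 of 64 or 8 of 80, which is about 3 or 4 per treatment. A model would then be fragile.

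**The case against.** The strongest reply is that zero degrees of freedom follows from one reading only. The plan does not adopt the class scheme of the earlier trial, and occluso-proximal lesions can differ among themselves, for instance in surfaces involved or in ICDAS score. The inclusion criterion is also worded per child, so it does not expressly bar treating another kind of lesion in an enrolled child. All of this stands. It means that the test cannot be called impossible outright, but it leaves the factor undefined.

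On pairing, a chi-square run separately within each treatment, with exactly one molar per child per treatment, would contain no within-child pairs. This also stands, but the plan specifies neither condition: eligibility allows more than two molars, and the sentence speaks of both treatments together.

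A reader might infer more than the documents support:
- *That other classes were certainly treated.* The section is written in the past tense, which may suggest that more than one type was recorded. It does not show it.
- *That class differences within a pair would confound the treatment comparison.* Teeth are randomised, so such differences would add noise and possible chance imbalance, not systematic bias.
- *That the Introduction's gap between classes, about 50% for Class I against about 15% for Class II (50 − 15 = 35 points), measures an error here.* Those are 24-month results from a trial in which each child received one technique. This trial examines restorations at 6 months in a split-mouth design. The figures show only that class can matter.

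Finally, cavity type is in no aim or outcome, which limits the weight of the point.

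**Conclusion.** The point holds in conditional form. If cavity type means lesion class, the factor is constant among eligible teeth and the test has 0 degrees of freedom at any sample size. If it varies, the named test disregards pairing within child and gives wrong error bars, by a variance factor between 1 − ρ and 1 + ρ with two molars per child and equal numbers at each level. The exception is a within-treatment table with one molar per child, which the plan does not describe.

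This rests on the inclusion criteria describing the treated teeth, on the split-mouth design being carried out as stated, and on some positive correlation between a child's molars. It affects a subsidiary analysis. On the occluso-proximal-only reading, the primary ART versus SMART comparison is not affected by this point. The change is worth making because the two sections cannot be read together as they stand and the remedy is cheap.

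**What to change.** Reconcile the inclusion criteria with the Statistical Analysis section, in one of these ways.

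- **Delete** the test of success by cavity type.
- **Or replace it.** Name a factor that can vary among eligible teeth and define its levels, for example ICDAS score 4 versus 5. State that the score is kept for each tooth; it is used for eligibility, but nothing says that it is retained. Analyse success by treatment and that factor with a method clustered on child, such as GEE logistic regression. Label it exploratory, and report counts and percentages only if cells are small.
- **If other cavity classes are in fact treated,** say so in the eligibility text and record class per tooth, so that within-pair differences in class can be described. Any analysis by class should also be clustered on child and labelled exploratory.

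If the analysis has already been run, state which levels were observed, how many molars and children were in each, and whether the treatments were pooled.

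Deleting the test costs one sentence. Replacing it costs a short paragraph and one retained variable per tooth. The last route also changes the eligibility text. The main downside of replacement is sparse data with 64 to 80 molars, which the descriptive fallback covers.
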